5.3. Derivations and Excluded Data

All data will be included for statistical analysis except data resulting from sample analyses that fail QC Biomarker assays or tests from different bioanalytical laboratories and employing different platform technologies will have different QC standards and metrics that are defined as part of the assay or test validation. Exclusion of biomarker data for statistical analysis will reflect pre-defined QC criteria, established prior to final analyses, as reflected in bioanalytical reports from the bioanalytical laboratory.

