7. DATA PREPARATION

7.1. Biomarker Sample Analysis

- Biomarkers measured in both archival tumor tissue and the de novo tumor biopsy may include, but may not be limited to, the following:
 - Targeted tumor DNA (TTD) NGS gene panel (Tempus xT; 595 gene panel);
 - Whole exome tumor DNA (WETD) NGS (Tempus Whole Exome Sequencing);
 - Targeted tumor RNA (TTR) panel (HTG 2560-transcript Oncology Biomarker Panel (OBP));
 - Whole transcriptome tumor RNA (WTTR) NGS (Tempus RNaseq);
- Biomarkers measured in blood may include, but may not be limited to, the following:
 - Targeted blood cfDNA (TBD) NGS gene panel (Guardant 360 and/or Guardant OMNI).

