7.2. Biomarker Data Management

Data generated by analytical laboratories will be delivered through secure FTP or through the best practices of the industry to ensure high level data protection. The data received will be stored in the sponsor's secure server.

Data QC document from each analytical laboratory will be delivered to the project team and stored in the sponsor's secure server. Additional QC will be performed by the computational biology team, and the QC methods will be defined in the supplemental statistical analysis plan.

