8.1.2. Statistical Methods for Categorical Variables

Regular Wald CIs suffer from low coverage probabilities that may be below nominal level. An improved CI estimation for the difference of proportions between matched pair will be employed (Agresti and Min, 2005; Tango 1998).^{1,4}

For n matched pairs on a binary response, denote the probability of outcome i for the first observation and outcome j for the second observation by π_{ij} , where outcome 1 = 'positive' and 2 = 'negative'. Denote the four corresponding sample proportions by $p_{11} = a/N$, $p_{12} = b/N$, $p_{21} = c/N$, and $p_{22} = d/N$. Let $\pi_1 = \pi_{11} + \pi_{12}$, $\pi_2 = \pi_{21} + \pi_{22}$. Denote the sample proportions of positives by p_1 and p_2 , $p_1 = p_{11} + p_{12}$, $p_2 = p_{21} + p_{22}$. Notations are illustrated in the table below:

| | Positive | Negative | Total |
|----------|---------------|--------------|---------------|
| Positive | $a (p_{11})$ | $b (p_{12})$ | $a + b (p_1)$ |
| Negative | $c (p_{21})$ | $d (p_{22})$ | $c + d$ |
| Total | $a + c (p_2)$ | $b + d$ | N |

For the matched pairs, the score interval consists of the set of $\Delta = \pi_1 - \pi_2$ values for which

$$\frac{|(p_2 - p_1) - \Delta|}{\sqrt{[(\hat{\pi}_{12}(\Delta) + \hat{\pi}_{21}(\Delta)) - \Delta^2]/n}} < z_{\alpha/2}$$

where $\pi_{jk}(\Delta)$ denotes the ML estimate of π_{jk} under the constraint that $\pi_1 - \pi_2 = \Delta$. There is not a closed-form expression for the resulting interval, but it can be obtained using iterative methods. The iteration stops when the score is close to $Z\alpha/2$ within defined margin 1e-06. The calculation of the score based interval can be performed with function scoreci.mp() in R package PropCIs or equivalent SAS macro program. McNemar test (mcnemar.test() in R or proc freq in SAS) will be used to compare the proportions between archival and de novo samples, and p values will be reported. For high dimensional data such as WES, RNASeq,

Gene panel etc., an FDR based method (qvalue package in R or proc multtest in SAS) may be used for multiplicity adjustment (Storey, 2015).³

For the CI estimation of proportion from one sample, Wilson score method will be used (Wilson, 1927). The calculation of the score based interval can be performed with function scoreci in R package PropCIs or proc freq in SAS.

$$\frac{\hat{p} + \frac{z^2}{2n}}{1 + \frac{z^2}{n}} \pm \frac{z}{1 + \frac{z^2}{n}} \sqrt{\frac{\hat{p}(1 - \hat{p})}{n} + \frac{z^2}{4n^2}}$$

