8.2. Statistical Analysis

8.2.1. Analysis of Primary Endpoint

The primary endpoint is the change in the frequency of gene alterations associated with disease progression. The analysis of primary endpoint will be performed on data set in the BET (TTD) and BET (WETD) population defined in [Section 5.2](#). As described in [Section 8.1.2](#), score based method and McNemar test will be used for CI estimation and hypothesis testing. For each gene alteration in each cohort, the frequency of alteration is calculated as # of patients who carry the alteration divided by the total number of patients in the cohort. For both archival and denovo samples in BET(WETD) and BET(TTD) population, the count of subjects carrying the alterations, estimates and 95% CI of the frequency of alterations, the change in the frequency of alterations, p values and qvalues of the change in frequency will be reported.

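### The primary-endpoint q-values have no testability filter, so alterations too sparse to reach significance enlarge the FDR family and cost power for smaller changes and smaller cohorts

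*SAP*

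**What the plan says.** SAP 8.2.1 analyses the primary endpoint row by row: "For each gene alteration in each cohort, the frequency of alteration is calculated as # of patients who carry the alteration divided by" the cohort total. It does so in both the targeted-panel and the exome populations, and states that "p values and qvalues of the change in frequency will be reported". SAP 7.1 lists the assays as "Targeted tumor DNA (TTD) NGS gene panel (Tempus xT; 595 gene panel" genes) and "Whole exome tumor DNA (WETD) NGS (Tempus Whole Exome Sequencing").

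On the test, SAP 8.1.2 says "McNemar test (mcnemar.test() in R or proc freq in SAS) will be used to compare the proportions between archival and de novo samples". It does not say whether the exact, continuity-corrected or uncorrected form is meant. On multiplicity it says "an FDR based method (qvalue package in R or proc multtest in SAS) may be used for multiplicity adjustment". That wording is optional, whereas the q-value statement in 8.2.1 is not.

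The only exclusion rule concerns assay quality (SAP 5.3): "All data will be included for statistical analysis except data resulting from sample analyses that fail QC". SAP 7.2 adds, for further checks by the computational biology team, that "the QC methods will be defined in the supplemental statistical analysis plan". That supplement is cited for QC only. Nothing sets a minimum count, says whether a row is a gene or a variant, or says whether panel and exome form one family or two. No q-value cut-off is given.

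**The concern.** McNemar's test uses only discordant pairs, that is, patients whose alteration status differs between the archival and the post-progression sample. Most genes on a broad panel change in very few patients. Such rows cannot give a small exact or continuity-corrected p-value whatever the direction of change, but each one adds to the multiplicity penalty on the rows that can.

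The q-value is the only multiplicity-adjusted result for the primary endpoint, and the primary objective is to identify markers of resistance. If the family is mostly untestable rows, a true marker of moderate frequency can get an unremarkable q-value because of how the family was formed rather than because of the data.

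**Working it through.** **1. The plan's own figures.** Protocol Table 2 gives precision only. The Tango score interval with b = n x difference gains and c = 0 losses reproduces all nine rows. For example, n=100 with b=10 gives 5.52% to 17.44% (printed 6%, 17%), and n=50 with b=10 gives 11.24% to 33.04% (printed 11%, 33%). The table therefore assumes markers with gains and no losses, and the same assumption is used below.

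**2. Which rows are testable.** With d discordant pairs all in one direction:
- Exact two-sided p = 2 x 0.5^d: d=5 gives 0.0625, d=6 gives 0.031.
- Continuity-corrected chi-square = (d-1)^2/d: d=5 gives p=0.074, d=6 gives p=0.041.
- Uncorrected chi-square = d: d=1 gives p=0.317, d=4 gives p=0.0455.

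Six pairs are needed with the first two forms and four with the third. R's mcnemar.test(), which the SAP names, applies the continuity correction by default and returns no p-value when there are no discordant pairs.

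**3. What family size costs.** A single top-ranked marker needs 2 x 0.5^g <= 0.05/m, where g is its number of gains and m the family size.
- m=595: threshold 0.05/595 = 8.4e-5, so g=15 (2 x 0.5^15 = 6.1e-5).
- m=60, for illustration: threshold 8.3e-4, so g=12 (2 x 0.5^12 = 4.9e-4).

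For n=100 and a true gain of 12%, the binomial chance of at least 15 gains is 22%, and of at least 12 gains 55%. For n=50 and 20%, the two chances are 6% and 29%.

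**4. Simulation.** Inputs from the documents: 595 genes (SAP 7.1); n=50 and n=100 (Protocol Table 1). Assumptions: one row per gene; background gain and loss rates equal within a gene, log-normal across genes with median 0.3% to 1% (log-SD 1); one marker without losses; q<0.05; rows with no discordant pair dropped; exact p-values. With this background, 83-98% of genes at n=100 and 94-99.6% at n=50 have fewer than 6 discordant pairs. Power ranges run over the two medians, with Monte Carlo error of a few points:

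| n, true gain | All rows with a discordant pair | Rows with b+c >= 6 |
|---|---|---|
| 100, 12% | 24-33% | 48-81% |
| 50, 20% | 14-17% | 44-89% |
| 50, 30% | 68-78% | 93-99% |
| 100, 20% | 92-95% | 98-100% |
| 50, 10% | about 0% | at most about 20% |

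Under the global null, the filtered procedure made any false call in at most about 2% of runs. With continuity-corrected p-values, unfiltered power in the first three lines falls to about 7-10%, 1-3% and 32-44%.

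**5. A different background.** A second model used mean discordance of 1-5%, one to five markers, continuity-corrected p-values in both arms, and all 595 rows in the unfiltered family. Power rose from about 0.5% to 9-91% (n=50, 20%), from 21-44% to 68-100% (n=50, 30%) and from 72-91% to 87-100% (n=100, 20%). The direction is the same, but the size depends strongly on the background.

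**6. Why the filter is valid.** Under no change, b given b+c is binomial with probability 1/2. The exact p-value conditions on b+c, so selecting rows on b+c does not distort it.

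**The case against.** A reader might infer that real resistance markers of the planned size will mostly be missed. The documents do not support that. Protocol 8.2 plans no effect size: it calls the work hypothesis-generating, and the 10%, 20% and 30% in Table 2 are illustrative observed changes. With exact p-values and no filter, power is already 92-100% for 20-30% changes at n=100 and 97-99% for 30% at n=75. Protocol Table 1 gives 100 patients to cohorts 3, 4 and 7, and 100 to cohorts 1 and 2 together; only the two prostate cohorts have 50 each.

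Nor is anything gated on q. SAP 4.1 and 4.2 state no formal testing and no decision rule. Counts, frequencies and changes appear for every alteration. The known mechanisms are also pre-specified secondary endpoints (SAP 8.2.3), whose listed outputs for alteration frequency are estimates and intervals, not q-values. All of this stands and limits the point. It does not remove it, because 8.2.1 still commits to reporting q-values.

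A second tempting inference is that variants seen in one patient will be flagged. That needs variant-level rows, uncorrected p-values and Storey estimation all at once. Every one-patient variant then has p=0.317 and the estimated null share collapses: to 0.03-0.14 with lambda 0.5, or 0.08-0.63 with the spline. Since q is about 0.317 x null share, that gives roughly 0.01-0.04 or 0.03-0.20. The SAP allows this combination but does not specify it: mcnemar.test() by default gives p=1 for such a row, and Benjamini-Hochberg fixes the null share at 1.

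Finally, that every alteration enters the family is the natural reading of 8.2.1 rather than an explicit statement, and the supplemental SAP was not available for review.

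**Conclusion.** The concern holds in a limited form. As written, the q-values carry a multiplicity penalty for rows that cannot reach significance, and the SAP leaves open the row unit, the family, the form of the McNemar test and the cut-off. The loss falls on smaller changes and smaller cohorts: power is roughly halved or worse for a 12% gain at n=100 and for a 20% gain at n=50, and is about 20 to 25 points lower for a 30% gain at n=50. It is small for 20-30% changes at n=100. The filter does not rescue 10% changes at n=50.

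These sizes rest on the assumed background, one marker without losses, gene-level rows and a 5% cut-off, none of which the SAP states. Losses in the marker would lower power in both arms. What does not depend on the background is the arithmetic of testability: fewer than 6 discordant pairs cannot give p<0.05 by the exact or corrected test.

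**What to change.** In SAP 8.1.2 and 8.2.1:
- Define the row as the gene, positive if it carries any qualifying alteration, and say what qualifies. With variant-level rows, few would reach six discordant pairs and the family could be nearly empty.
- Define the FDR family per cohort and per assay.
- Restrict the family to rows with at least 6 discordant pairs (b+c >= 6).
- Use exact conditional McNemar p-values with Benjamini-Hochberg. This also removes the risk of a collapsed Storey null share.
- Report sparser rows descriptively, with counts and score intervals.
- State the q-value cut-off. The minimum of 6 matches 5%; at 10% the matching minimum would be 5, since 2 x 0.5^5 = 0.0625.
- Align the optional FDR wording in 8.1.2 with the firm commitment in 8.2.1.

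The cost is a few sentences and a few lines of code, with no new data. Rows with fewer than 6 discordant pairs get no q-value, but nothing is lost at 5%: a Benjamini-Hochberg q is never below its p-value, which for those rows is at least 0.0625.

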8.2. Statistical Analysis

8.2.1. Analysis of Primary Endpoint

The primary endpoint is the change in the frequency of gene alterations associated with disease progression. The analysis of primary endpoint will be performed on data set in the BET (TTD) and BET (WETD) population defined in [Section 5.2](#). As described in [Section 8.1.2](#), score based method and McNemar test will be used for CI estimation and hypothesis testing. For each gene alteration in each cohort, the frequency of alteration is calculated as # of patients who carry the alteration divided by the total number of patients in the cohort. For both archival and denovo samples in BET(WETD) and BET(TTD) population, the count of subjects carrying the alterations, estimates and 95% CI of the frequency of alterations, the change in the frequency of alterations, p values and qvalues of the change in frequency will be reported.

8.2.2. Analysis of Secondary Endpoints

Summary statistics will be generated for the secondary endpoints. For the proportion of patients with fully evaluable archival and post progression tumor biopsies, proportions and 95% CI will be calculated using the method described in [Section 8.1.2](#). For the overall agreement rates of gene mutations between post progression biopsy tissue and blood NGS results, basic summary statistics such as mean, median, and range of count of alterations per patient across all patients will be generated for each cohort. In addition, mean and median count of alterations in agreement between biopsy and blood samples will be calculated for each cohort. The frequency of alterations detected from post progression biopsy tissue, blood and the corresponding 95% CIs will be generated. In the BE (TBD) and BET (TBD) population, the concordance between both matched biopsy tissue and blood samples and the 95% CI and Cohen's Kappa will also be calculated to evaluate the agreement.

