## 2. STUDY OBJECTIVES AND ENDPOINTS

Primary Objective:	Primary Endpoint:

To obtain and analyze archival pre-treatment tumor samples and post-progression tumor biopsies to identify molecular markers of resistance to selected anti-cancer therapies.

	

Change in the frequency of gene alterations between pre-treatment tumor samples and post-progression tumor biopsies.

Secondary Objectives:	Secondary Endpoints:

To evaluate the success rate in obtaining paired archival and post-progression tumor biopsies that are adequate to meet the objectives of the study;

To determine concordance in gene alterations identified by NGS analysis of post-progression tumor tissue and blood.

	

Proportion of patients with fully evaluable archival and post-progression tumor biopsy (eg, sample sufficient for all intended analyses at all measured time points);

Overall agreement rates of gene alterations between post-progression biopsy tissue and blood NGS results.

Secondary Objectives by Target Biology:	Secondary Endpoints by Target Biology:

PD-1-L1 inhibition:
 
 
To evaluate alterations in genes encoding HLA, <math>\beta</math>2-Microglobulin, Signal transducer and activator of transcription 1(STAT1), JAK1, JAK2, IFN-<math>\gamma</math>, and interferon-gamma receptor (IFNGR) as mechanisms of resistance to PD-1/PD-L1 checkpoint blockade.
 
	
 
Change in the frequency of alterations in genes encoding HLA, <math>\beta</math>2-Microglobulin, STAT1, JAK1, JAK2, IFN-<math>\gamma</math> and IFN-<math>\gamma</math>R between pre-treatment archival and post-progression samples;
 
The frequency of alterations in genes encoding HLA, <math>\beta</math>2-Microglobulin, STAT1, JAK1, JAK2, IFN-<math>\gamma</math> and IFNGR in cfDNA.
 

CDK4/6 inhibition:
 
 
To evaluate alterations in the Rb gene as a mechanism of resistance to palbociclib.
 
	
 
Change in the frequency of RB1 gene alterations between pre-treatment archival and post-progression samples.
 
The frequency of RB1 gene alterations in cfDNA.
 

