5.2. Biomarker Evaluable Patient Analysis

The Biomarker Evaluable (BE) population is defined as patients in the SA population who have at least one biomarker result from analysis of collected biospecimen. The fully biomarker evaluable (FBE) population is defined as the patients in the SA population who have every biomarker result from analysis of collected biospecimen.

The Biomarker Evaluable Target (BET) population is defined as patients in the BE population who have a targeted tumor DNA panel biomarker result from both the archival and de novo biopsy tumor tissue biospecimen.

Additional subset populations include:

- BET (TTD), defined as all patients in the BET population who have results of targeted tumor DNA (TTD) NGS gene panel sample analysis from both the archival and de novo biopsy tumor tissue biospecimen.
- BET (TTR), defined as all patients in the BET population who have results of targeted tumor RNA (TTR) sample analysis from both the archival and de novo biopsy tumor tissue biospecimen.
- BET (WETD), defined as all patients in the BET population who have results of whole exome tumor DNA (WETD) NGS sample analysis from both the archival and de novo biopsy tumor tissue biospecimen.

- BET (WTTR), defined as all patients in the BET population who have results of whole transcriptome tumor RNA (WTTR) NGS sample analysis from both the archival and de novo biopsy tumor tissue biospecimen.

■ CCI

- BET (TTD-TTR), defined as all patients in the BET population who have both evaluable targeted tumor DNA (TTD) NGS gene panel data and targeted tumor RNA (TTR) sample analysis from both the archival and de novo biopsy tumor tissue biospecimen.
- BE (TBD), defined as all patients in the BE population who have results of targeted blood cfDNA (TBD) NGS gene panel sample analysis from the post- progression blood sample.
- BET (TBD), defined as all patients in the BET population who have results of targeted blood cfDNA (TBD) NGS gene panel sample analysis from the post- progression blood sample.

[figure not shown]

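### SAP 8.2.2 plans tissue-blood agreement with no positive percent agreement, no stated unit or denominator and no shared-gene rule, on patient sets that do not fit the comparison

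*SAP*

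**What the plan says.** - **Endpoint.** Protocol section 2 names it as "Overall agreement rates of gene alterations between post-progression biopsy tissue and blood NGS results". SAP 6.1 repeats it.
- **Assays.** SAP 7.1 lists for tissue "Targeted tumor DNA (TTD) NGS gene panel (Tempus xT; 595 gene panel", plus whole exome sequencing, and for blood "Targeted blood cfDNA (TBD) NGS gene panel (Guardant 360 and/or Guardant OMNI". Blood may therefore be read on either of two panels or on both. The genes and alteration types those panels report are not listed.
- **Measures.** SAP 8.2.2 plans per-patient alteration counts, and says that "mean and median count of alterations in agreement between biopsy and blood samples will be calculated for each cohort". It continues: "The frequency of alterations detected from post progression biopsy tissue, blood and the corresponding 95% CIs will be generated". For BE (TBD) and BET (TBD) it adds: "the concordance between both matched biopsy tissue and blood samples and the 95% CI and Cohen's Kappa will also be calculated". Concordance has no formula.
- **Patient sets.** SAP 5.2 gives "BE (TBD), defined as all patients in the BE population who have results of targeted blood cfDNA (TBD) NGS gene panel sample analysis". Entry to BE itself requires only that they are "patients in the SA population who have at least one biomarker result from analysis of collected biospecimen". BET (TBD) requires targeted tumour DNA results from both archival and de novo tissue, plus a cfDNA result.
- **cfDNA frequencies.** SAP 8.2.3 runs every analysis in its Table 3, including the cfDNA frequencies, on BET (TTD) and BET (WETD).
- **Exclusions.** SAP 5.3 removes data only when the sample analysis fails QC.

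**The concern.** The objective is to learn how far blood sequencing reproduces what the post-progression biopsy shows. The direct answer is the proportion of tissue-positive results that are also blood-positive, and that proportion is not among the planned outputs. An overall agreement rate credits every result that is negative in both samples. For uncommon alterations that is nearly all of them, so the rate can be high for a blood test of no value.

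Two further gaps affect any agreement measure, kappa included. Nothing limits the comparison to genes and alteration types that both assays report, and blood panels may differ between patients. And the named patient sets are not the patients who have both a de novo tissue result and a cfDNA result. If definitions are settled only once data are in hand, the reported agreement depends on choices the plan leaves open.

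**Working it through.** The documents give no expected value or precision for tissue-blood agreement. Protocol Table 2 concerns change between archival and post-progression tissue and does not bear on this point.

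**Step 1. Overall agreement against detection.** For one alteration let a = positive in both, b = tissue only, c = blood only, d = negative in both, n = a+b+c+d.
- Overall agreement OA = (a+d)/n
- Positive percent agreement PPA = a/(a+b)
- Kappa = (OA − pe)/(1 − pe), with pe the chance agreement from the two margins

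Take c = 0 (assumption), so OA = 1 − prevalence × (1 − PPA). Prevalences are illustrative. Protocol 1.1.2.1 calls RB1 mutations rare, and Protocol 1.1.3.2 cites AR amplification at 15% to 30%.

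| Tissue prevalence | PPA | OA | Kappa | Double negatives as share of agreement |
|---|---|---|---|---|
| 5% | 0% | 95.0% | 0 | 100% |
| 5% | 50% | 97.5% | 0.655 | 97.4% |
| 10% | 0% | 90.0% | 0 | 100% |
| 10% | 50% | 95.0% | 0.643 | 94.7% |
| 30% | 0% | 70.0% | 0 | 100% |
| 30% | 50% | 85.0% | 0.583 | 82.4% |

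Worked row (5%, PPA 50%, n = 100): a = 2.5, b = 2.5, d = 95. OA = 97.5/100 = 0.975. pe = 0.05 × 0.025 + 0.95 × 0.975 = 0.9275. Kappa = (0.975 − 0.9275)/0.0725 = 0.655.

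At 5% prevalence, then, OA moves only from 95% to 97.5% as detection goes from none to half. Kappa moves from 0 to 0.655.

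**Step 2. Can PPA be recovered from the planned outputs?** Yes, per alteration, if all outputs use the same patients: a/n = (OA − 1 + p_tissue + p_blood)/2. For the worked row, (0.975 − 1 + 0.05 + 0.025)/2 = 0.025, and 0.025/0.05 = 50%. The frequency sentence in 8.2.2 names no population, so a common set is not assured.

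**Step 3. Genes only one assay reports, and undetectable tumour DNA.** All inputs here except the 595 genes are assumptions: 5 tissue alterations per patient, no blood-only calls, and true detection of 80% where blood can report the gene and tumour DNA is present. Let s be the share of tissue alterations reportable in blood and f the share of patients with detectable tumour DNA. If unreportable genes were scored negative, apparent PPA = s × f × 0.8 and OA = 1 − (5/595)(1 − PPA).
- s = 25%, f = 60%: PPA 12%, OA 99.3%, kappa 0.21
- s = 50%, f = 80%: PPA 32%, OA 99.4%, kappa 0.48
- s = 100%, f = 100%: PPA 80%, OA 99.8%, kappa 0.89

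True detection is the same in all three. OA barely moves; kappa moves for reasons unrelated to how well blood detects what it can report.

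**Step 4. Patient sets.**

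| Set | De novo tissue result required? | cfDNA result required? | Assigned to |
|---|---|---|---|
| BE (TBD) | No | Yes | Concordance (8.2.2) |
| BET (TBD) | Yes, and archival too | Yes | Concordance (8.2.2) |
| BET (TTD), BET (WETD) | Yes, and archival too | No | cfDNA frequencies (8.2.3) |

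The comparison needs de novo tissue plus cfDNA. BE (TBD) asks for less and BET (TBD) for more. The sets given for cfDNA frequencies can contain patients with no cfDNA result. The only frequency formula, in 8.2.1 for the primary endpoint, divides by everyone in the cohort.

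**Step 5. Precision of PPA.** Wilson 95% intervals at an observed 80%: 4/5 gives 37.6% to 96.4%; 8/10 gives 49.0% to 94.3%; 16/20 gives 58.4% to 91.9%. Five tissue positives is what 5% prevalence yields in 100 patients.

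**The case against.** **Kappa and both marginal frequencies are planned.** A reader might infer that the analysis cannot show whether blood finds the tissue alterations. The documents do not support that: kappa separates the cases in Step 1, and Step 2 recovers PPA on a common patient set. This stands. What remains is that PPA is not itself reported, has no interval, and its recovery depends on an unstated population.

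**The count of agreeing alterations is not inflated by double negatives.** On its natural reading it counts detected alterations only. Its defect is the missing denominator and shared-gene rule. Double-negative dominance follows only if concordance is computed as simple overall agreement, which the endpoint's name suggests but no formula confirms.

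**No text scores an off-panel gene as negative.** SAP 7.3 rules out imputing missing values, and an unreported gene can be read as missing. Nor does 8.2.2 say that exome results enter the agreement analysis. Both points stand, so Step 3 shows what could happen without a rule, not what the SAP prescribes.

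**Patients without tumour DNA in plasma.** A reader might infer that they count as true negatives for every gene. They do not: for each tissue-positive gene they are tissue-only disagreements. Agreement in all patients, including these, is a legitimate quantity.

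**Matched samples.** 8.2.2 describes matched tissue and blood, which implies pairs. That helps for concordance, but conflicts with naming BE (TBD) and does nothing for 8.2.3.

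**Text not visible.** Redacted blocks follow 8.2.3, and the SAP version history mentions a further agreement analysis. The point is therefore confined to the visible specification of this secondary endpoint. The supplemental plan cited in SAP 7.2 is described as covering QC methods.

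**Weight.** The endpoint is descriptive, and SAP 4.1 plans no formal hypothesis test.

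**Conclusion.** The concern holds as a specification gap. SAP 8.2.2 leaves the unit and denominator of agreement open, omits positive percent agreement, and has no rule for genes only one assay reports. If concordance is simple overall agreement, it reads 95% at 5% prevalence and 90% at 10% when blood detects nothing, assuming no blood-only calls. Kappa exposes this but does not correct for differing panels. The misfit of patient sets in 8.2.2 and 8.2.3 follows from the definitions in SAP 5.2 and needs no assumption.

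The effects of panel overlap and undetectable tumour DNA cannot be sized from the documents. The apparent PPA range of 12% to 80% in Step 3 rests wholly on assumed inputs. The conclusion is that the analysis as specified does not reliably report detection in blood, not that its results would be uninterpretable.

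**What to change.** 1. **SAP 8.2.2, population and scope.** State the unit (gene, variant or patient) and the denominator. Analyse patients with both a de novo tissue result and a cfDNA result, limited to genes and alteration types reportable by both the tissue panel and the blood panel used for that patient.
2. **SAP 8.2.3, cfDNA frequencies.** Use as denominator the patients with a cfDNA result on a panel that reports the gene.
3. **Measures.** Make positive percent agreement, its reverse (blood-positive also tissue-positive) and negative percent agreement the main concordance measures, with the Wilson intervals already adopted in SAP 8.1.2. Keep overall agreement and kappa as supportive.
4. **Detectable tumour DNA.** Keep the all-patient result as main. A repeat in patients with at least one somatic cfDNA alteration is an optional sensitivity analysis. Label it as selecting on a positive blood result, which inflates apparent detection.

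**Cost.** SAP wording and a list of reportable genes and alteration types from the laboratories; no new data. Protocol section 8 lets the SAP modify planned analyses and asks for a protocol amendment only for major changes to the primary endpoint or its analysis. The downside is smaller denominators, wide intervals for rare alterations (Step 5) and less flattering figures than overall agreement.
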